## LIST OF ABBREVIATIONS

Abbreviation or Term 	Definition/Explanation
AE	Adverse event
ALT	Alanine aminotransferase
ANCOVA	Analysis of covariance
ANOVA	Analysis of variance
APTT	Activated partial thromboplastin time
AST	Aspartate aminotransferase
AV	Atrioventricular
β-HCG	Beta-human chorionic gonadotropin
BID	Twice daily
BLQ	Below limit of quantification
BMI	Body mass index
BP	Blood pressure
BUN	Blood urea nitrogen
Ca ++	Calcium
CBC	Complete blood count
CFR	Code of Federal Regulations
CHF	Congestive heart failure
CI	Confidence interval
Cl-	Chloride
CL cr	Creatinine clearance
C max	Maximum observed concentration
C min	Trough observed concentration
CNS	Central nervous system
CR	Complete response
CRF	Case report form
CT	Computed tomography
CTCAE	Common Toxicity Criteria for Adverse Events
CV	Coefficient of variation
CYP	Cytochrome P450
D/C	Discontinue
ECOG	Eastern Cooperative Oncology Group
eCRF	Electronic case report form

Abbreviation or Term 	Definition/Explanation
DLT	Dose Limiting Toxicity
ECG	Electrocardiogram
Eg	Exempli gratia (for example)
FACS	Fluorescence Activated Cell Sorting
FDA	Food and Drug Administration
FDG-PET	Fluorodeoxyglucose (FDG)-positron emission tomography (PET)
GCP	Good Clinical Practice
GFR	Glomerular filtration rate
GGT	Gamma glutamyl transferase
GLP	Good laboratory practice
HBsAg	Hepatitis B surface antigen
HBV	Hepatitis B virus
HCO 3 	Bicarbonate
HCV	Hepatitis C virus
HIV	Human immunodeficiency virus
HR	Heart rate
hr	Hour or hours
IC 50	Half maximal inhibitory concentration
i.e.	Id est (that is)
IEC	Independent ethics committee
INR	International normalized ratio
IRB	Institutional review board
IU	International unit
IV	Intravenous, intravenously
LDH	Lactate dehydrogenase
LLQ	Lower limit of quantitation
MedRA	Medical Dictionary for Drug Regulatory Activities
MRI	Magnetic resonance imaging
MRSD	Maximum recommended starting dose
MTD	Maximum tolerated dose
NOAEL	No-observed-adverse-effect level
NOEL	No-observed-effect-level
PD	Pharmacodynamic(s)
PFS	Progression Free Survival

Abbreviation or Term 	Definition/Explanation
PK	Pharmacokinetic(s)
PO	Per os (administered by mouth)
PR	Partial response
PT	Prothrombin time
PTT	Partial thromboplastin time
QC	Quality control
RBC	Red blood cell
QD	Once daily
QTc	QT interval corrected
QTcF	QT interval corrected using Fredericia equation
SAE	Serious adverse event
SD	Standard deviation or stable disease
T 1/2	Terminal elimination half-life
T 3	Triiodothyronine
T 4	Thyroxine
T max	Time of maximum observed concentration
TID	Three times daily
TSH	Thyroid-stimulating hormone
ULN	Upper limit of normal
ULQ	Upper limit of quantitation
UV	Ultraviolet
WBC	White blood cell
WOCBP	Women of childbearing potential
WONCBP	Women of non-childbearing potential

All of these abbreviations may or may not be used in protocol.

**Name of Institution**

## STUDY SUMMARY

Title	Pembrolizumab for the treatment of recurrent high grade neuroendocrine carcinoma
Short Title	Pembro NEC
Protocol Number	IRB#102310
IND	IND Exempt
Phase	Phase 2
Design	Open label, non-randomized with subjects receiving 200mg Pembrolizumab to assess response rate in patients with NEC.
Study Duration	Accrual anticipated over 30 months, time to complete 42 months
Study Center(s)	This trial will open as a multi-site study conducted at the Huntsman Cancer Institute-University of Utah (including various other satellite sites and Intermountain Healthcare).
Objectives	To assess overall response rate, clinical benefit rate, progression free survival and overall survival in patients that receive Pembrolizumab using irRECIST
Number of Subjects	30 – 40 total
Diagnosis and Main Eligibility Criteria	High grade (Grade 3 defined by Ki-67 >20% or >20 mitoses/10 hpf) non-pulmonary neuroendocrine carcinoma. Patients must have failed at least one line of therapy but no maximum number of therapies is exclusionary (i.e. second-line therapy and beyond)
Study Product, Dose, Route, Regimen	Pembrolizumab 200 mg IV q3weeks
Duration of administration	24 months
Reference therapy	none
Statistical Methodology	Simon two-stage design based on expected RR of 25%.

## SCHEMA

## 1 OBJECTIVES

### 1.1 Primary Objectives and Endpoint

To evaluate overall response rate of pembrolizumab (irPR + irCR) using immune related (ir)RECIST in patients with non-pulmonary, high grade neuroendocrine carcinoma.

### 1.2 Secondary Objectives and Endpoint

- 1.2.1 To evaluate clinical benefit rate of pembrolizumab (irPR + irCR + irSD) using irRECIST in this setting.
- 1.2.2 To evaluate progression free survival of patients treated with pembrolizumab in this setting.
- 1.2.3 To evaluate the median overall survival (OS) of patients treated with pembrolizumab in this setting
- 1.2.4 To evaluate safety and tolerability of the pembrolizumab in this setting.

### 1.3 Exploratory Objectives and Endpoint

- 1.3.1 To evaluate the correlation of response to tumor mutational burden.
- 1.3.2 To evaluate the correlation of response to PD-L1 expression in primary tumor.
- 1.3.3 To evaluate the correlation of response to proliferative rate in Grade 3 NECs (Ki-67 20-55% vs. Ki-67 >55%).

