### 2.2 Neuroendocrine carcinoma (NECs) / Neuroendocrine Tumors (NETs)

Neuroendocrine tumors (NETs) make up a relatively rare but heterogeneous family of neoplasms. Historically considered rare, the incidence of NETs has been steadily increasing since the 1970s, with SEER registry data suggesting an increase in incidence of almost 500% over this period of time in the United States (1). These tumors arise from neuroendocrine cells that are found primarily in the gut and make up the largest group of hormone-producing cells in the body. The hallmark of NETs is evidence of predominant neuroendocrine differentiation; namely, they have distinctive morphologic characteristics and expression of specific tissue markers including chromogranin A, synaptophysin, and neuron-specific enolase. These tumors commonly arise in the lung, intestine and pancreas but can arise in various anatomic locations including the larynx, thymus, kidneys, cervix, prostate, ovaries, and other sites. No primary site is identified in approximately 10 – 15% of metastatic NET cases (1).

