## 9 STUDY CALENDAR

**CYCLE** Calendar: 1 cycle = 21 days ( $\pm$  3 days)

Examination	Screening 	C1 	C2	C3	C4	C5	C6	C7 and beyond	End of Treatment	Follow-up 
Informed consent	X									
Medical history/baseline AE	X									
Eligibility criteria	X									
Vital signs	X	X	X	X	X	X	X	X	X	
Physical examination	X	X	X	X	X	X	X	X	X	X
ECOG performance status	X	X	X	X	X	X	X	X	X	
Hematology 	X	X	X	X	X	X	X	X	X	
Chemistry 	X	X	X	X	X	X	X	X	X	
Urinalysis	X								X	
T3, free T4, TSH 	X				X			X 		
PT, PTT, INR	X									
Pregnancy test 	X									
Review Adverse events and events of clinical interest		X	X	X	X	X	X	X	X	
Review of concomitant medications	X	X	X	X	X	X	X	X		
Archival tissue for PD-L1 analysis 	X									
Archival tissue for TMB analysis 	X									
Archival tissue for Ki-67 analysis 	X									
ECG 	X									
CT scans (c/a/p) 	X			X		X		X 	X	X 
Disease Assessment (irRECIST) 	X			X		X		X	X	X
MRI 										
Study drug 		X	X	X	X	X	X	X		

- 1 ALL Pre-study/Screening procedures should be completed within 4 weeks of study enrollment - with the exception of laboratory tests which need to be completed within 14 days prior to study enrollment.
- 2 Hematology includes CBC with differential and platelets
- 3 Chemistry includes Albumin, Alkaline Phosphatase, Aspartate Aminotransferase, Alanine Aminotransferase, Total Bilirubin, Calcium, Carbon Dioxide, Creatinine, Chloride, Glucose, Potassium, Protein, Sodium, and Urea Nitrogen
- 4 T3, free T4, TSH to be performed at screening and every 9 weeks (every third cycle) while on treatment
- 5 Pregnancy test must be done at screening and within 72 hours of starting study treatment for all women of childbearing potential and repeated as clinically indicated. Serum or urine tests may be used. If urine pregnancy is positive, confirm with serum.
- 6 If the patient consented to the optional testing and tissue is available (either from archival tissue or fresh biopsy tissue), PD-L1 analysis will be performed at central lab. If fresh tissue is being used, it should be obtained during screening window prior to study treatment. See section 15.

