## 10 STUDY PROCEDURES

### 10.1 Screening Evaluations

- Informed Consent
- Physical examination with vital signs and ECOG Performance Status
- Review of medical history/baseline symptoms
- Review baseline concomitant medications
- Laboratory assessments:
  - CBC with differential
  - CMP to include sodium, potassium, chloride, carbon dioxide or bicarbonate, blood urea nitrogen (BUN), creatinine, glucose, total protein, albumin, calcium, AST, ALT, alkaline phosphatase, total bilirubin
  - Coagulation to include PT/INR and aPTT
  - Thyroid function tests to include TSH, total T3, and free T4
  - Serum or urine pregnancy test (for women of childbearing potential) within 72 hours of starting study treatment
  - Urinalysis
- 12-lead ECG if clinically indicated
- CT scans and disease assessments for baseline irRECIST
- MRI only for subjects with previously treated brain metastases
- Archival tissue or fresh tissue biopsy (if archival tissue is not available) for Ki-67 testing (see footnote #8 in calendar)
- Archival tissue or fresh biopsy for central PD-L1 analysis if patients consent to optional testing.

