## **12 STATISTICAL CONSIDERATIONS**

A Simon Optimum Two-Stage design will be used with a Type I error rate alpha equal to 0.10 and a Type II error rate beta equal to 0.20. The null hypothesis is an objective response rate (irCR + irPR) of 10% or lower. The alternative hypothesis is an objective response rate of 25% or higher. With these design parameters, the first stage will consist of 13 patients. If there are 2 or more responses in 13 patients, up to an additional 21 evaluable patients will be recruited for a maximum sample size of 34 evaluable patients. If there are 6 or more responses in up to 34 evaluable patients the null hypothesis will be rejected. If there are 5 or fewer responses 34 evaluable patients the null hypothesis will not be rejected. It is estimated that it may be necessary to enroll up to 40 patients to accrue 34 response evaluable patients.

Kaplan-Meier methods and associated confidence intervals will be used to analyze PFS and OS. All subjects assessed for progression will contribute to this analysis. The clinical benefit rates (irCR + irPR + irSD) will be analyzed by tabulating the observed counts and proportions together with exact binomial confidence intervals.

Tumor tissue will be analyzed for the correlation of biomarkers to response rate.

- 1) Tissues analyzed for correlation of tumor mutational burden will be categorized as high, medium and low burden.
- 2) Tissues analyzed for correlation of PD-L1 expression will be categorized as high or low.
- 3) Tissues analyzed for correlation to proliferative index will be categorized as Ki-67 20-55% or Ki-67 > 55%.

Fisher's exact test will be used to analyze each of these biomarkers. Two sided p-values < 0.05 will be regarded as statistically significant.

Safety will be analyzed by tabulating adverse events.

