## **15 SPECIAL INSTRUCTIONS**

### **15.1 Pathology review for PD-L1 analysis at central laboratory**

Formalin fixed paraffin embedded (FFPE) tissue samples will be sent for PD-L1 IHC analysis at screening if samples are available. Fine needle aspirate, frozen sample, plastic embedded sample, cell block, clot, bone, bone marrow or cytologic specimens will not be accepted for PD-L1 IHC analysis. If a patient does not have archival tissue available and a fresh biopsy is required for Ki-67 testing (see 15.3), tissue will be sent for PD-L1 analysis if adequate tissue is available after Ki-67 testing has been performed. This is optional when tissue is available for evaluation.

If the patient consents to this testing, screening tissue samples will be sent to QualTek Molecular Laboratories.

Please reference the Qualtek lab manual for more information.

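### Objective 1.3.2 concerns PD-L1 in the primary tumor, but the tissue rules do not require primary tissue, and Section 12 reduces PD-L1 to high or low at a cut the protocol does not state

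*Combined protocol and SAP*

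**What the plan says.** - **Objective.** Section 1.3, item 1.3.2, sets out to correlate response with "PD-L1 expression in primary tumor".
- **Tissue.** Footnote 6 of the Section 9 calendar applies to consenting patients: if "tissue is available (either from archival tissue or fresh biopsy tissue), PD-L1 analysis will be performed at central lab". Section 10.1 lists "Archival tissue or fresh biopsy for central PD-L1 analysis if patients consent to optional testing". Where a fresh biopsy was needed for Ki-67, Section 15.1 says "tissue will be sent for PD-L1 analysis if adequate tissue is available after Ki-67 testing has been performed". Section 15.1 asks for FFPE samples, refuses several specimen types (aspirates, frozen, cell block, bone and cytologic material among them), and refers to the central laboratory's manual. It does not refuse metastases.
- **Population.** Inclusion 5.1.1 admits metastatic or unresectable disease. Section 2.2 says: "No primary site is identified in approximately 10 – 15% of metastatic NET cases".
- **Analysis.** Section 12: "Tissues analyzed for correlation of PD-L1 expression will be categorized as high or low". Each biomarker is tested against response with Fisher's exact test, and two-sided p below 0.05 is called significant. In the same list, Ki-67 has a numeric cut (20–55% against above 55%); PD-L1 has none.

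**The concern.** There are two separate issues.

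The first is what is measured. If part of the tissue is metastatic, a report written to objective 1.3.2 would describe primary-tumor PD-L1 from a mixture of sites. For a patient with no identified primary, the quantity named in the objective does not exist.

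The second is how it is tested. An ordered score is cut in two at a point that the protocol does not give. A cut fixed early leaves a valid test but discards information in a small sample. A cut settled late, in an open-label trial where responses are known as they occur, could be influenced by the responses, and the 0.05 level would then no longer describe the test.

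**Working it through.** **1. Objective against tissue rules.** The restriction to the primary appears only in 1.3.2. Footnote 6, 10.1 and 15.1 limit consent, tissue availability and specimen type, but not anatomical site. Some samples may be from the primary, so the match is not ruled out; it is simply not ensured.

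For scale, apply the 10–15% of Section 2.2 to the 34–40 patients of Section 4.2: 0.10 × 34 = 3.4 and 0.15 × 40 = 6.0, so roughly 3–6 patients without an identified primary. This is an assumption: the rate is for metastatic NET in general, not previously treated high-grade NEC, and the denominator ignores that PD-L1 testing is optional.

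**2. The plan's own figures.** Inputs from Section 12: 13 then 34 patients, continue on 2 or more responses, reject on 6 or more, rates 10% and 25%.
- P(stop at stage 1 | 10%) = 0.9^13 + 13 × 0.1 × 0.9^12 = 0.2542 + 0.3672 = 0.621.
- P(reject) = sum over x ≥ 2 of P(X = x in 13) × P(Y ≥ 6 − x in 21). This gives 0.0957 at 10% and 0.8108 at 25%.

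The design reproduces (alpha 0.10, power 80%). The plan gives no size or power for the PD-L1 test beyond the nominal 0.05.

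**3. One cut fixed in advance.** Take 34 tested, 6 responders and a median split of 17 and 17. If all 6 responders fall in one half, p = 2 × C(17,6)/C(34,6) = 2 × 12,376/1,344,904 = 0.018. A 5–1 split adds 2 × 17 × C(17,5)/C(34,6) = 2 × 17 × 6,188/1,344,904 = 0.156, so p = 0.175. Only the 6–0 split is significant, and the true size is 1.8%. Averaged over the number of responders, the size at a median cut is about 2% at a 25% response rate and about 1% at 10%. No single cut tried at n = 34 exceeded 5.0%.

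**4. A cut searched after responses are known.** PD-L1 ranks are taken as independent of response. The calculation is the chance that the smallest two-sided Fisher p over the candidate cuts is below 0.05, averaged over Binomial(34, response rate).

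| n = 34, candidate cuts | 25% response | 10% response |
|---|---|---|
| Untied score, cuts within 20–80% of patients | 16.7% | 10.3% |
| Untied score, cuts within 10–90% | 21.2% | 13.3% |
| Untied score, all cuts | 22.5% | 14.1% |
| Six score levels, 20–80% | 7.1% | 3.9% |
| Four score levels, 20–80% | 5.1% | 2.8% |
| Three score levels, 20–80% | 4.3% | 2.9% |

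The score levels are assumed; the documents give no scale. Restricting an untied score to quartile cuts gives 5–6%. With fewer tested (untied, 25%, cuts within 20–80%) the figure is 14.0% at 25 patients, 11.4% at 20 and 9.3% at 15. Selection by the stage 1 rule was not modelled.

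**5. Using the ordered score.** An exact Wilcoxon rank-sum test of score against response stays at or below 5% under the null, with or without ties. Assume that a random responder outscores a random non-responder on the underlying score with probability 0.75 (AUC), with 34 tested and a 25% response rate:
- Fisher at a pre-set median split: about 28% power.
- Exact Wilcoxon, coarse tied score: about 49–57%.
- Exact Wilcoxon, untied score: about 59–60%.

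With 24 tested and an untied score, the figures are about 16% (Fisher) and 42% (Wilcoxon).

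**The case against.** The strongest reply is that little here is an error in the plan. The objective is exploratory. Fisher's test at a fixed cut is valid, and Section 12 uses it for all three biomarkers. The laboratory manual cited in 15.1 may define both score and cut, and it is not among the documents. Nothing says that the cut will be chosen after looking at responses. The power comparison rests on an assumed AUC and a median cut, neither of which is in the plan.

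Much of this stands, and it rules out three stronger readings that a reader might infer:
- *The analysis cannot answer the objective.* Not supported: archival tissue may be from the primary, and a primary-only subset could be analysed where the site is known.
- *The 5% test really runs at about 17%.* Not supported: that needs a search over many cuts after responses are known, an untied score, all 34 patients tested and a response rate near 25%. It is neither a property of the plan nor an upper limit.
- *The sampled site is not recorded.* This cannot be judged: the case report forms and the manual were not supplied. The protocol simply does not ask for the site.

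What the reply does not remove is the wording conflict between 1.3.2 and the tissue rules, which a cut in the manual would leave untouched, and the loss of power from splitting the score.

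**Conclusion.** The point holds as a minor one. The tissue rules do not secure what objective 1.3.2 names, and this follows from the text alone. The size of the mismatch is unknown; 3–6 patients without an identified primary is only indicative, and metastatic samples from patients with a known primary would add to it.

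On the test, the PD-L1 cut is absent from the protocol but may exist in the manual. If it is fixed in advance, the error is controlled and the cost is power, which roughly halves under the stated assumptions. If it were searched for afterwards, the error at n = 34 would range from about 3–7% (three to six score levels) to about 10–22% (untied score), depending on response rate and the range of cuts. That is a possibility left open, not something planned. No decision rule uses PD-L1, so the stopping rule and the primary response-rate conclusion stand.

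**What to change.** 1. Reword 1.3.2 to *PD-L1 expression in the tumor tissue tested (primary or metastasis)*. Report the sampled site with the result, adding it to the specimen form if it is not already captured.
2. In Section 12, test the recorded PD-L1 score against response with an exact Wilcoxon rank-sum test that allows ties.
3. Keep high/low as a descriptive table, at a cut-off fixed before PD-L1 is linked to response. State the scoring method and cut, or cite the version of the laboratory manual that sets them.

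Cost: a few lines of text, at most one form field, and no extra tissue. One exploratory test will differ from those for the other biomarkers, and the central laboratory must report the score itself, not only the category.

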## 2 BACKGROUND

### 2.1 Hypothesis

Pembrolizumab will be clinically active in patients with high grade NECs as demonstrated by clinical response

### 2.2 Neuroendocrine carcinoma (NECs) / Neuroendocrine Tumors (NETs)

Neuroendocrine tumors (NETs) make up a relatively rare but heterogeneous family of neoplasms. Historically considered rare, the incidence of NETs has been steadily increasing since the 1970s, with SEER registry data suggesting an increase in incidence of almost 500% over this period of time in the United States (1). These tumors arise from neuroendocrine cells that are found primarily in the gut and make up the largest group of hormone-producing cells in the body. The hallmark of NETs is evidence of predominant neuroendocrine differentiation; namely, they have distinctive morphologic characteristics and expression of specific tissue markers including chromogranin A, synaptophysin, and neuron-specific enolase. These tumors commonly arise in the lung, intestine and pancreas but can arise in various anatomic locations including the larynx, thymus, kidneys, cervix, prostate, ovaries, and other sites. No primary site is identified in approximately 10 – 15% of metastatic NET cases (1).

## 2.3 NET / NEC Classification and Grading

The pathologic classification of non-pulmonary neuroendocrine malignancies is complex and continually evolving. Low grade, well-differentiated neuroendocrine neoplasms are commonly referred to as “neuroendocrine tumors” (NETs) whereas high grade, poorly differentiated neuroendocrine neoplasms are commonly referred to as “neuroendocrine carcinoma” (NECs). Pathologic specimens are distinguished based on morphologic evidence of differentiation. Well-differentiated NETs show a solid, trabecular, gyriform, or glandular pattern with uniform nuclei, salt-and-pepper chromatin, and finely granular cytoplasm. Poorly differentiated NECs resemble small cell or large cell neuroendocrine carcinoma of the lung. Small cell NECs are comprised of small round cells with small amounts of cytoplasm with hyperchromatic nuclei; large cell NEC cells are arranged in organoid, trabecular, or palisading patterns with prominent necrosis.

The 2010 WHO classifications of gastroenteropancreatic neuroendocrine tumors (GEP-NETs) adopted a classification system previously endorsed by the European Neuroendocrine Tumour Society (ENETS). Namely, well-differentiated tumors are separated into low-grade and intermediate-grade with poorly-differentiated tumors generally classified as high grade depending on mitotic count and/or Ki-67 proliferation indices (Table 1). The WHO Grade 3 (G3) of NECs is somewhat heterogenous. Namely, the majority of NECs exhibit a poorly differentiated morphology and will fall in the range of G3 tumors based on mitotic or proliferative indices; however, a subset of patients will exhibit a well- or moderately-differentiated histology but higher grade based on mitotic and proliferative indices. These tumors are considered “grade discordant.” Their clinical behavior generally falls somewhere between lower grade NETs and poorly differentiated, G3 NECs.

**Table 1: 2010 WHO tumor grading for gastrointestinal neuroendocrine tumors**

Grading of GEP-NETs	Mitotic Index	Ki-67 labelling index
Grade 1 (G1)	<2 mitoses/10 hpf	≤2%
Grade 2 (G2)	2-10 mitoses/10 hpf	3-20%
Grade 3 (G3)	>20 mitoses / 10 hpf	>20%

Well-differentiated NETs are frequently associated with clinical syndromes depending on hormone secretion. Namely, NETs arising in the small bowel are often associated with “carcinoid syndrome,” manifest by diarrhea, flushing, palpitations, wheezing and other symptoms predominantly due to excess serotonin secretion. Similarly, pancreatic NETs may secrete insulin, glucagon, gastrin, vasoactive intestinal peptide (VIP), somatostatin, or other hormones with clinical syndromes directly related to this hormone secretion. On the other hand, poorly differentiated NECs do not closely resemble non-neoplastic neuroendocrine cells and are not generally associated with specific clinical syndromes due to excessive hormone secretion. Like SCLC, however, poorly differentiated are relatively frequently associated with other paraneoplastic syndromes (e.g. hypercalcemia, hyponatremia, venous thromboembolism, etc.).

